**The below describes procedures if Hospital Study Day 1 assignment was the JUUL e-cigarette.**

### Pre PK – Baseline Assessments

- At 8 AM, the participant will be admitted to the research ward
- First morning urine void will occur at 8 AM and participant will be hydrated
- Breakfast will be served between 8:30-9:00 AM
- Expired CO will be measured to ensure the participant did not smoke any tobacco cigarettes
  - If the expired CO is  $\leq$ 5ppm, the participant will receive a \$50 cash bonus
  - If the expired CO is  $>$ 5ppm, the CRC must notify the PI (or co-I's) immediately. A decision on how to proceed will be based on PI discretion.
- At about 9 AM, an intravenous catheter will be placed in the forearm for blood sampling
- **Baseline questionnaires** will be collected after IV placement: MNWS, QSU ("no cig")
- CRC will weigh the JUUL e-cigarette with the pod in the device pre-vaping
- At approximately 9:15 AM, a blood sample will be collected for **baseline plasma nicotine**
- At approximately 9:15 AM, a blood sample will be collected for **baseline plasma catecholamines**
- At approximately 9:15 AM, a urine sample will be collected for **baseline total nicotine equivalents and VOC measurements**
- At approximately 9:15 AM, a heart rate and blood pressure will be measured 10 minutes before vaping session
- At approximately 9:24, a heart rate and blood pressure will be measured 1 minute before vaping session

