### PK Collection

- The CRC will weigh the JUUL after the puffing protocol is complete
- Blood samples will be collected at 2, 5, 7, 10, 15, 30, 60, 90, 118 minutes post end vaping session for **plasma nicotine**
- **Heart rate** will be collected at 2, 5, 7, 10, 15, 30, 45, 60, 75, 90, 100, 118 minutes post end vaping session
- **Blood pressure** will be collected at 5, 10, 15, 30, 45, 60, 75, 90, 100, 118 minutes post end vaping session
- Blood sample will be collected at 5 minutes post end vaping session for **plasma catecholamines**
- Urine Sample will be collected at 118 minutes post end of vaping session
- **Questionnaires** administered at **5, 10, 15, 30, 45, 60, and 120 minutes** post end vaping session: Henningfield Drug Liking Assessment; **5 minutes** post end vaping session: MNWS, QSU, mCES; **118 minutes** post end vaping session: MNWS, QSU("no cig")
- Lunch will be served around 11:30 AM, following the 118 min blood draw

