Statistical Analysis Plan: Evaluating the Comparative Pharmacokinetics of Nicotine after administration via JUUL or Tobacco Cigarettes

June 9, 2020

Protocol Number: 19-28309

Grant Number: R01DA039264

[name] (PI)

[name], PhD (Co-I)

Summary of Protocol

Description and Outcome Measures

This is an observational, crossover design that will examine the pharmacokinetics and pharmacodynamics of smoking tobacco cigarettes compared to vaping the JUUL electronic cigarette. Participants will be recruited in two groups: primary e-cigarette vapers and primary cigarette smokers. The order of assignment to either tobacco cigarettes or the JUUL electronic cigarette will be counter-balanced. We will seek to enroll 30 participants total (15 in each group).

The following schedule of events describes the study procedures:

Study Day – Tobacco Cigarette Condition	Study Day – JUUL E-Cigarette Condition
Day 1	Day 2
←----- HOSPITAL -----→	

• Baseline Blood Draws
• 1 nicotine 6ml blood draw• 1 catecholamine 6ml blood draw• Baseline Urine Nicotine and VOCs• Baseline Heart Rate• Baseline Blood Pressure• 1st Standardized Session• 2-hr abstinence and biological samples and measurements
• 9 nicotine 6ml blood draws• 12 heart rate measurements• 10 blood pressure measurements• 1 urine sample• 1 catecholamine 6ml blood draw• 4-hr recorded ad libitum use and biological samples and measurements
• 8 nicotine 6ml blood draws• 1 urine sample	
• Baseline Blood Draws
• 1 nicotine 6ml blood draw• 1 catecholamine 6ml blood draw• Baseline Urine Nicotine and VOCs• Baseline Heart Rate• Baseline Blood Pressure• 1st Standardized Session• 2-hr abstinence and biological samples and measurements
• 9 nicotine 6ml blood draws• 12 heart rate measurements• 10 blood pressure measurements• 1 urine sample• 1 catecholamine 6ml blood draw• 4-hr recorded ad libitum use and biological samples and measurements
• 8 nicotine 6ml blood draws• 1 urine sample

Power Calculation & Sample Size

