Our power analysis based on a 2-condition within-subject repeated measures comparison. To estimate the required sample size the minimal power level was set at 80% and Type I error at 0.05, with use of a 2-sided test. The primary outcome on which we have powered the study is the difference in nicotine exposure for JUUL vs tobacco cigarette use. We used prior within-subject variability data on plasma cotinine (mean 200 ng/ml, coefficient of variation, COV 25%) in TC smokers whose cotinine had been measured on multiple occasions for estimation. For 15 participants, we have 80% power to detect an effect size ratio of 1.25 for daily nicotine exposure.

[figure not shown]
Trial Management

Study Site & Timetable

Participant visits will be conducted at Zuckerberg San Francisco General Hospital (ZSFG) at both the Tobacco Research Center and the Clinical Research Services Research Ward.

The projected study timetable is as follows:

Timeline	Specific Aim
Preparation (Months 1-2)	
• Study startup (supply purchasing, case report form and database completion)• Clinical Research Coordinator & CTSI staff training• Participant Recruitment
Clinical Study (Months 3-12)	
• Recruit, enroll and complete study procedures on approximately 2-4 participants per month• Conduct online analytical chemistry assays• Conduct ongoing data entry and quality assurance
Analysis (Months 9-12)	
• Complete data entry, analysis and manuscript preparation• Complete analytical chemistry assays

Targeted Population

We will seek to complete a total of N=30 randomized participants. We will seek to enroll equal numbers of men and women, and all minority groups will be invited to participate. At a minimum we will enroll 25% women in the sample (about N=5). We will not enroll minors or those under tobacco purchasing product age (21 years) in the state of California.

Data Acquisition and Transmission

Data capture will occur in several ways. Identifying information will be stored locally at UCSF in a secure database and/or locked secure files. General recruitment and enrollment information, such as dates of screening and enrollment will be stored in a password protected Excel database supported by Information and Technology (IT) at UCSF.

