The first step in the analysis will be examining the collected data using graphical analysis and descriptive summaries to ensure that all are within expected ranges, to check for the presence of outliers and abnormal values, and to ascertain that the distribution of all measures meets the assumptions of the statistical tests to be used. Means of the outcome measures will be tested for equality using a repeated measures model. Tests will include, in addition to treatment condition, a test for order to determine possible carry-over effects. Estimation will be done using full-information maximum likelihood methods so that we can use all data in estimation even if some are missing. Analyses will primarily be conducted using SAS 9.4. More specifically, the analyses for each sub-aim are described below:

Specific Aim 1: We will determine from the standardized sessions the plasma nicotine peak concentration, time to peak concentration and area under plasma nicotine concentration-time curve (AUC) and compare JUUL vs. tobacco cigarette conditions using a mixed-effect

model for cross-over. We will also compute ratios of AUC values for the two conditions, as is commonly done in comparing the pharmacokinetics of different pharmaceutical products. The ratio of AUCs will give us information on relative nicotine doses obtained from JUUL vs. tobacco cigarettes.

Specific Aim 2: We will perform the same analysis as Specific Aim 1, but with plasma nicotine concentrations from the ad libitum periods.

Specific Aim 3: With standardized sessions, we will use a paired t test to compare peak changes in heart rate, and changes in plasma norepinephrine and epinephrine concentration, and pulmonary function tests (FEV1, FVC, FEV1/FVC).

Specific Aim 4: Satisfaction, psychological reward, unpleasant effects and withdrawal symptoms will be compared using a mixed effects model for cross-over data average measures from the mCEQ, the QSU and the MNWS for the JUUL e-cigarette and tobacco cigarette conditions.

Quality Assurance

Procedures in place to ensure the validity and integrity of the data

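### Aim 3 tests catecholamine changes with a paired t test, which fixes the weight on one pre-use sample at 1; estimating that weight would cost little and could gain precision

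*SAP*

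**What the plan says.** Under Data Analysis Plan, Specific Aim 3, the SAP states that for the standardized sessions "we will use a paired t test to compare peak changes in heart rate, and changes in plasma norepinephrine and epinephrine concentration". It names no baseline covariate, no period term and no measurement scale.

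The opening paragraph of the same section is broader: "Means of the outcome measures will be tested for equality using a repeated measures model", with treatment condition and a test for order. It names no baseline covariate either. The SAP then turns to the individual aims. Aims 1 and 4 are given mixed-effects crossover models, and Aim 2 follows Aim 1. Only Aim 3 is given a paired t test.

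The sampling is the same in both documents. Protocol section 6.5 (Pre PK – Baseline Assessments) places the catheter first: "At about 9 AM, an intravenous catheter will be placed in the forearm for blood sampling". At about 9:15 AM a sample is drawn for "baseline plasma catecholamines". Under PK Collection the protocol says: "Blood sample will be collected at 5 minutes post end vaping session for" plasma catecholamines. The SAP schedule lists "1 catecholamine 6ml blood draw" at baseline and again after the session, in each condition. So each person has one pre-use and one post-use value per product.

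**The concern.** In a parallel-group trial, subtracting the baseline removes differences between people. In a crossover, the JUUL-minus-tobacco difference has already removed them. What remains in the product difference of the pre-use values is day-to-day variation plus assay and sampling error. The change score subtracts that remainder with a weight of 1. If the remainder predicts the post-use difference only weakly, subtraction adds noise to the contrast.

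With one pre-use draw per day, nothing averages that noise down. The total sample is 30, and the documents give no power calculation for catecholamines. An avoidably wide interval would make an inconclusive result on a named Aim 3 outcome more likely.

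**Working it through.** **The plan's own figure.** The SAP's only power statement concerns nicotine exposure: "Type I error at 0.05, with use of a 2-sided test", 80% power, n = 15, ratio 1.25, mean 200 ng/ml, coefficient of variation 25%. On the raw scale the difference is 0.25 × 200 = 50, the within-subject SD is 50 and the SD of a paired difference is √2 × 50 = 70.7. The normal approximation gives Φ(50/(70.7/√15) − 1.96) = Φ(0.78) ≈ 78%, so the figure is roughly reproduced. The exact t calculation gives 72%. Neither says anything about catecholamines.

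**Inputs.** From the documents: one pre-use and one post-use sample per condition, n = 30 in total or 15 per user group, two-sided 5%. Assumed, because the documents do not give them:
- r, the correlation between the product differences in pre-use values (Dbase) and post-use values (Dpost)
- k = SD(Dpost)/SD(Dbase)

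**Formulas, in units of Var(Dpost).**
- Change score (slope fixed at 1): 1 + 1/k² − 2r/k
- Adjusted contrast (slope estimated), large samples: 1 − r²
- Excess of the change score: 1/k² − 2r/k + r² = (1/k − r)², which is never negative and is zero when r × k = 1
- Cost of estimating the slope: multiply the adjusted variance by (n − 2)/(n − 3), which is 28/27 = 1.037 at n = 30 and 13/12 = 1.083 at n = 15

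**Equal SDs (k = 1).** Var(change)/Var(adjusted) = [2/(1 + r)] × (n − 3)/(n − 2). The last column gives the power of the change score at n = 30 where the adjusted analysis has 80% (noncentral t, n − 1 against n − 2 degrees of freedom).

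| r | n = 30 | n = 15 | Change-score power, n = 30 |
|---|---|---|---|
| 0.2 | 1.61 | 1.54 | about 60% |
| 0.5 | 1.29 | 1.23 | about 70% |
| 0.8 | 1.07 | 1.03 | about 77% |

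At n = 30 the standard errors are √1.61 = 1.27, √1.29 = 1.13 and √1.07 = 1.04 times as wide. At r = 0.5 the change score would need about 30 × 1.286 ≈ 39 participants to match 30 with adjustment.

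**Break-even at k = 1.** Setting the ratio to 1 gives r = 2(n − 3)/(n − 2) − 1. This is 54/28 − 1 = 0.93 at n = 30 and 24/13 − 1 = 0.85 at n = 15. Above these values adjustment loses slightly.

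**Unequal SDs (n = 30, r = 0.5).**
- k = 0.7: (1 + 2.041 − 1.429)/0.75 × 27/28 = 2.07
- k = 1.5: (1 + 0.444 − 0.667)/0.75 × 27/28 = 1.00
- k = 2: (1 + 0.25 − 0.5)/0.75 × 27/28 = 0.96

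**Adding a period term.** The multiplier becomes (n − 3)/(n − 4): 27/26 = 1.038 at n = 30 and 12/11 = 1.091 at n = 15, taking sequences as balanced. The ratios above hardly change.

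**The case against.** The strongest objection is that the gain is unknown and may be nil. The large figures depend on k = 1. One sample follows overnight abstinence and the other follows nicotine, so post-use differences could well vary more than pre-use ones. At n = 15 and r = 0.5 the ratio is already 0.96 at k = 1.5 and 0.92 at k = 2. This stands. A reader might infer that the change score loses unless the pre/post correlation is very high, or that adjustment is free. The documents support neither: the result turns on r × k, and estimating a slope has a cost. Nor is subtraction always worse than ignoring the baseline when r is below 0.5. The threshold is 1/(2k), which is 0.25 at k = 2.

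A reader might also infer that a catheter placed 15 minutes before the draw shows the baseline to be noisy. The documents give no such variability, and placement is scheduled alike on both days.

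It can further be said that the paired t test is standard and unbiased, that catecholamines are not the primary outcome, and that the SAP's general paragraph already names a repeated measures model. The first two stand and limit the weight of the point. The third does not answer it, because that paragraph names no baseline covariate and Aim 3 then specifies its own test.

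Uncertainty about r and k does not favour a fixed slope. The possible loss is small and bounded, while the possible gain is much larger.

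**Conclusion.** The point holds as a matter of precision. Aim 3 fixes at 1 a slope that the data could estimate. With equal SDs, the variance penalty at n = 30 runs from 61% at r = 0.2 through 29% at r = 0.5 to 7% at r = 0.8. It is about zero, or slightly in favour of the change score, where r × k is near 1. These are ranges under assumed r and k, not estimates for this trial.

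The comparison also assumes that the expected pre-use values are the same on both product days, so that the two analyses target the same contrast. Counterbalanced order makes this reasonable but does not prove it.

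A reader might take this to mean that the planned test is invalid or its error rate wrong. It does not: the planned test is unbiased for the mean difference in change. The improvement is worth making before results are seen because it is cheap and the choice of covariate is then not open to hindsight.

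**What to change.** In Aim 3, for norepinephrine and epinephrine, take the 5-minute post-use value as the outcome in the mixed crossover framework used for Aims 1 and 4. Include product, period and sequence, and enter the same-day pre-use value as two covariates: the person's mean over the two days and the deviation from that mean. Alternatively, regress each person's product difference in post-use values on the product difference in pre-use values plus a sequence term, which carries the period effect. Without that term the regression does not correspond to the crossover model.

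Keep the paired t test on changes as a stated sensitivity analysis.

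Cost: SAP wording only, with no new samples, visits or participants. The product contrast loses one degree of freedom for the slope and one for period (n − 3 against n − 1). If the true slope is near 1, its variance rises by about 4% at n = 30 and 8–9% at n = 15.

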### 2.3 SPECIFIC AIM #3

To evaluate various outcomes following JUUL e-cigarette or tobacco cigarette use, both with standardized and ad lib use including: heart rate, plasma catecholamines, pulmonary function testing.

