### Ad Lib Use (12 PM – 4 PM)

- At approximately 12:00 PM , a 4 hour ad lib video taped session will begin and participants will be allowed to use the JUUL as they wish
- CRC will weigh the JUUL e-cigarette before ad lib begins
- **Questionnaires** administered half-way through ad lib at approximately **1:30PM**: MNWS, QSU, mCES; **5, 10, 15, 30, 45, 60, and 120 minutes** post ad lib start: Henningfield Drug Liking Assessment
- Blood samples will be collected every 30 minutes during ad lib at 12:30 PM, 1:00 PM, 1:30 PM, 2:00 PM, 2:30 PM, 3:00 PM, 3:30 PM & 4:00 PM for **plasma nicotine**
- Urine Sample will be collected at 195 minutes into Ad Lib session
- **Final questionnaires** administered at 3:50 PM: MNWS, QSU, mCES, Overall Drug Liking Assessment, GRPQ for JUUL, Utility of E-Cigs Questionnaire
- CRC obtains final weight of JUUL e-cigarette
- At 4:00pm the participant is discharged from the hospital ward

## 6.6 HOSPITAL STUDY DAY 2

In most cases, hospital study day 2 will occur directly after study day 1, however if it is more convenient for the participant to reschedule to a later time, they can complete study day 2 between 2 days and up to one week from study day 1. **The below describes procedures if Hospital Study Day 1 assignment was the JUUL vaping.**

The tobacco cigarette ARM will differ from the JUUL e-cigarette ARM in the following ways:

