### Ad Lib Use

- CRC will provide tobacco cigarettes based on participant's normal brand and cigarettes per day
- CRC will weigh a standard reference tobacco cigarette before ad lib begins
- CRC obtains final weight of all tobacco cigarette butts
- At the end of the day, **final questionnaires** will be administered: Overall Drug Liking Assessment, GRPQ for tobacco cigarettes
- Regardless of which product was assigned, on Hospital Study Visit 2, the participant will also take the following as part of their final questionnaires: Difficulty Quitting, Purchase Tasks, Stiles Intent to Use Product Again

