Data will be acquired via participant self-report and in a combination of paper source documentation transcribed into electronic data capture (EDC) by clinical research staff, and by direct entry into EDC by participants. Medical history data will be collected as paper source and will remain paper source and not entered. Demographics, nicotine & tobacco product use, drug use and nicotine dependence recorded at baseline will be entered by the participant directly into EDC, and there will be no paper source files. Physiological measures such as blood pressure, urine tox and pregnancy test results will

be recorded on a paper CRF and entered into the EDC. Adverse events will be recorded on an AE log. This paper source log will be entered into the EDC. Questionnaires completed during the study on craving, satisfaction and emotions will be entered by the participant directly into EDC. Cardiovascular data will be downloaded from the ambulatory blood pressure monitor into a PDF, which will be transcribed into Excel and uploaded directly into EDC. Video files from the recorded adlib sessions will be transferred from the camcorder to an encrypted hard drive that will be stored in a secured locked cabinet accessible by study staff only. All source documents will be stored in participant binders. Data management activities will be performed using REDCap.

REDCap is a suite of software tools, supported by UCSF, which enables the collection, cleaning and viewing of clinical trial data. The database will be designed by the study team and once approved by the Investigator, Statistician, and Clinical Research Coordinator (CRC), the database will be put into production and data entry will begin. Data can be entered and changed only by those with the rights to do so. Varying interfaces allow for the CRC to view and enter data in a database format, and for the research participant to respond to questionnaires directly through electronic data capture.

REDCap has all capability to be compliant with 21CFR Part 11 and all relevant technical aspects of relevant GCP guidelines and allows for the following:

- The system can generate accurate copies of stored data and audit trail information in human readable form.
- System access is limited to authorized individuals through the controlled assignment of unique ID and password combinations.

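### Aim 3 names lung function and ad lib outcomes for which neither document records a measurement time; a smaller point is that its paired t test leaves out the order term and maximum likelihood stated for the outcome measures

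*SAP*

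**What the plan says.** Protocol section 2.3 sets Aim 3 as outcomes after use of either product, "both with standardized and ad lib use including: heart rate, plasma catecholamines, pulmonary function testing". So it covers three outcomes in two sessions.

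The SAP (Data Analysis Plan, Specific Aim 3) limits itself to the standardized sessions. It names a paired t test for peak changes in heart rate and for "changes in plasma norepinephrine and epinephrine concentration, and pulmonary function tests (FEV1, FVC, FEV1/FVC". Aims 1, 2 and 4 name a mixed-effects crossover model instead, and Aim 2 covers the ad lib periods explicitly. The opening paragraph of the same section plans, for the outcome measures generally, a repeated measures model, a test for order and full-information maximum likelihood. It then moves to the detail for each aim.

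Protocol section 6.5 (PK Collection) gives the times after the standardized session. Heart rate "will be collected at 2, 5, 7, 10, 15, 30, 45, 60, 75, 90, 100, 118 minutes post end vaping session". For catecholamines, "Blood sample will be collected at 5 minutes post end vaping session for" that assay. In the ad lib session, "Blood samples will be collected every 30 minutes during ad lib at 12:30 PM" and half-hourly to 4 PM, for plasma nicotine. Urine, questionnaires and product weights are also listed. The tobacco day (section 6.6) is written as differences from the JUUL day; its ad lib additions are of the kind "CRC obtains final weight of all tobacco cigarette butts". The ad lib part of the SAP schedule lists "8 nicotine 6ml blood draws" and one urine sample.

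**The concern.** An outcome that has an aim and an analysis but no measurement time cannot be produced by following the plan. Lung function is in that position. An outcome promised for ad lib use, with no time point there and no analysis of its own, is a stage further back. A later reader could not tell whether a missing Aim 3 result was never measured or was measured and not reported. The stake is the scope of Aim 3. The nicotine comparisons, and the power calculation that rests on nicotine exposure, are not affected.

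The t test is a lesser matter. It is the one aim-level method that does not deliver the order test or the use of incomplete data that the SAP states for the outcome measures.

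**Working it through.** **1. Tracing each outcome to a scheduled measurement.** The sources are protocol sections 6.2 (screening), 6.3 (orientation), 6.5 and 6.6 (study days), and the SAP schedule of events.

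| Outcome | Standardized session: before / after use | Ad lib session | Analysis specific to Aim 3 |
|---|---|---|---|
| Heart rate | 2 / 12 | 0 | standardized only |
| Catecholamines | 1 / 1 | 0 | standardized only |
| Lung function | 0 / 0 | 0 | standardized only |

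The two heart rate readings before use are at 10 minutes and 1 minute before the session. The SAP schedule counts 12 heart rates and 1 catecholamine draw in the two hours after the standardized session. These match the protocol's list exactly, so none is left over for ad lib use. The ad lib session has 8 plasma nicotine samples.

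Of the 3 × 2 = 6 cells, 2 have both data and an analysis specific to Aim 3 (heart rate and catecholamines, standardized). One has an analysis but no documented data (lung function, standardized). The three ad lib cells have no documented data and no analysis specific to Aim 3.

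**2. What the paired t test costs.** The documents give no period effect on these change scores, so the effect below is an assumed range.

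- Model for participant i: D = δ + π in one order and δ − π in the other, plus normal error with SD 1. D is the JUUL minus tobacco difference in change from baseline.
- n = 30 complete pairs, 15 per order. The first 30 entries of the protocol's allocation list contain 15 of each sequence.
- Bias of the mean difference: π × (15 − 15)/30 = 0.
- Residual sum of squares: noncentral chi-square with 29 df and noncentrality 30π². The expected variance estimate is therefore 1 + (30/29)π², which is 1.00, 1.06, 1.26 and 2.03 at π = 0, 0.25, 0.5 and 1.0.
- δ = 0.529 SD, chosen to give 80% power at π = 0, two-sided 0.05.

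| π (SD of the paired difference) | 0 | 0.25 | 0.5 | 1.0 |
|---|---|---|---|---|
| Paired t test, power | 80% | 78% | 73% | 50% |
| Paired t test, type I error | 5.0% | 4.4% | 2.9% | 0.6% |
| With period term (28 df), power | 79.9% | 79.9% | 79.9% | 79.9% |

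The t test becomes conservative, and does not reject too often. A shift that raises or lowers a whole day, baseline and post-use values alike, cancels in the change from that day's baseline and costs nothing. Power is lost only if period alters the response itself.

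**The case against.** The schedules are visibly incomplete, so absence from them is weak evidence. The protocol's staff duties mention a physical examination at admission that the study-day procedures do not list. Skin blood flow and expired CO are in the protocol but not in the SAP schedule. The SAP says "Cardiovascular data will be downloaded from the ambulatory blood pressure monitor into a PDF", yet the protocol's procedures do not mention that device, and it might record heart rate through the ad lib hours. The SOPs that the documents cite are not included. Much of this stands: a reader might infer that lung function is not measured, or that Aim 3 cannot be delivered, and the documents do not show that. They show only that no time point is recorded in either document. The monitor's wear times are not stated, and it could not supply catecholamines or spirometry.

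A reader might also infer that the ad lib outcomes have no planned analysis at all. That goes too far, because the general repeated measures sentence could be read to cover them. What is missing is an analysis specific to Aim 3, together with the data to put into it.

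On the t test, one can argue that specific text overrides general text, so nothing is contradicted, or that the general text supplements it, so the order test is already promised. Either reading is possible, and a reader should not infer that the t test is invalid. The reason to change it is that a better method is already named for the other aims at almost no cost.

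**Conclusion.** The concern holds as a documentation gap in Aim 3. Lung function has no recorded measurement in either session, and heart rate and catecholamines have none in the ad lib session. Two of the six cells can be reported from the plan as written. Heart rate and catecholamine changes after the standardized session are scheduled and testable.

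The t test is secondary. Its power figures are illustrative. They rest on an assumed period effect, normal differences, 30 complete pairs and 15 participants per order. The fall to 50% needs a period effect of one full SD of the paired difference, and nothing in the documents suggests one that large. If the completers were unbalanced by order, a small bias would return: at 17 and 13 it would be π × 4/30 = 0.13π. A reader might carry the figures over to one user group of 15. The documents do not support that, because the SAP plans no group-specific Aim 3 analysis and the allocation list is not split by group.

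**What to change.** **Reconcile protocol section 2.3, the SAP schedule of events and SAP Aim 3.** If lung function and ad lib heart rate and catecholamines are already measured, enter their time points in both schedules and state the ad lib analysis. If they are not, remove lung function from Aim 3 in both documents, and remove the ad lib wording from protocol Aim 3. SAP Aim 3 contains no ad lib wording to remove.

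**In SAP Aim 3, replace the paired t test** with the mixed-effects crossover model named for Aims 1, 2 and 4. Use product, period and sequence as fixed effects and participant as a random effect. Participants with one study day then contribute.

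**Cost.** The first change is a protocol modification through the IRB. Under the SAP's section on changes or amendments, a change that needs IRB review also goes to NIH for approval before it is implemented. One that significantly alters the scope, or the ability to meet the aims, goes to the DSMB as well. The second is one SAP sentence and one residual degree of freedom (29 to 28). With 30 pairs and no period effect that is 80.0% − 79.9% = 0.1 point of power.

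### Aim 4 does not use the same-day pre-use QSU and MNWS scores that the protocol already collects, which costs precision in the JUUL versus tobacco comparison

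*SAP*

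**What the plan says.** The Aim 4 analysis is one sentence in the SAP's Data Analysis Plan: the two product conditions are compared with a "mixed effects model for cross-over data average measures from the mCEQ, the QSU and the MNWS". No time point, baseline term or change score is named. The general paragraph above it gives the only model terms: "Tests will include, in addition to treatment condition, a test for order to determine possible carry-over effects". Aim 3, in the same section, does use changes: it will "compare peak changes in heart rate, and changes in plasma norepinephrine and epinephrine concentration".

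Protocol 6.5 (Hospital Study Day 1, JUUL day) schedules QSU and MNWS at five times:

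- **Before use** (Pre PK – Baseline Assessments): baseline questionnaires "will be collected after IV placement: MNWS, QSU", the QSU carrying a no-cig tag.
- **5 minutes after the standardized session** (PK Collection): "post end vaping session: MNWS, QSU, mCES".
- **118 minutes after the session** (PK Collection): MNWS and QSU, the QSU again tagged no-cig. The SAP's schedule of events describes this interval as "2-hr abstinence and biological samples and measurements".
- **Mid ad lib** (Ad Lib Use): MNWS, QSU and mCES, "administered half-way through ad lib at approximately" 1:30 PM.
- **End of ad lib** (Ad Lib Use): MNWS, QSU and mCES at 3:50 PM.

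The mCES, which the SAP calls mCEQ, is never scored before use. Protocol 6.6 lists how the tobacco day differs. The baseline questionnaires are not on that list, so a same-day pre-use QSU and MNWS score exists for both products.

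**The concern.** Aim 4 asks how each product affects craving and withdrawal. A person's level on arrival can differ between the two hospital days. Participants are told not to smoke from 10 PM the night before (Protocol 6.3), but the CO check on admission detects smoking and not vaping, and readings above 5 ppm are left to the PI's discretion. The pre-use score measures that day-to-day difference directly and costs nothing more to collect. Without it, the difference stays in the residual.

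The undefined average raises a second, conditional issue. If it is taken over times and includes the pre-use score, a rating that cannot reflect that day's product becomes part of the product outcome.

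**Working it through.** **The plan's own figure.** None is given for Aim 4. The SAP's only power statement concerns nicotine exposure: 15 participants, 80% power, ratio 1.25, mean 200 ng/ml, COV 25%. With a difference of 0.25 × 200 = 50 and an SD of the paired difference of √2 × 50 = 70.7, the normal approximation gives n = (70.7 × (1.96 + 0.84) / 50)² ≈ 15.7, so 16, and 78.2% power at 15. That agrees closely with the stated figure, though an exact paired t calculation gives n = 18. Nothing below depends on it.

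**Assumed inputs.** The documents give no SD or correlation for QSU or MNWS. Let *r* be the correlation between ratings in their within-person, between-day differences. It is taken as 0.3 to 0.5, with equal variances. Let *k* be the share of the direct-use product effect still present at 118 minutes, from 0 to 1.

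**1. What leaving out the covariate costs (single post-use score).** Adjustment multiplies the residual variance by 1 − r²:

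| r | Variance factor, covariate | Interval width, √(1 − r²) | Variance factor, change score, 2(1 − r) |
|---|---|---|---|
| 0.3 | 0.91 | 0.954 (about 5% narrower) | 1.40 |
| 0.5 | 0.75 | 0.866 (about 13% narrower) | 1.00 |

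A change score does worse than no adjustment below r = 0.5 and only breaks even there. The covariate never has the larger variance factor.

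**2. Whether the omission biases the contrast.** The first 30 rows of the allocation table in Protocol 6.3 hold 15 participants in each sequence. Day-to-day differences in arrival level therefore add noise and do not systematically favour either product.

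**3. Dilution, only if the average covers all five times.** Three ratings follow direct use (5 minutes, mid ad lib, end ad lib), one carries a share *k*, and the pre-use rating carries none. The retained effect in scale points is (3 + k)/5:

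- k = 0: 3/5 = 60%.
- k = 1: 4/5 = 80%.

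If only the pre-use rating is dropped, the share is (3 + k)/4 = 75% to 100%.

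**4. The offset from averaging.** A five-score mean has variance (1 + 4r)/5 relative to one score: 0.44 at r = 0.3 and 0.60 at r = 0.5. The standardized effect relative to a single unadjusted 5-minute score is [(3 + k)/5] / √[(1 + 4r)/5]:

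- k = 0: 0.60/0.663 = 0.90 (r = 0.3) and 0.60/0.775 = 0.77 (r = 0.5).
- k = 1: 0.80/0.663 = 1.21 (r = 0.3) and 0.80/0.775 = 1.03 (r = 0.5).

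So the shrinkage in scale points is offset in part when no effect remains at 118 minutes, and fully in power terms when all of it does. The estimate in scale points is still too small.

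**The case against.** The strongest case against is that the SAP is under-specified here and not shown to be wrong. The averaging phrase covers the mCEQ as well, which has no pre-use score, so item or subscale means fit the sentence at least as well as means over time. The protocol labels the pre-use scores as baseline, and no passage puts them into the product mean. Aim 4 does not require change from a same-day baseline. The no-cig tag is unexplained and may mark a different QSU form. Splitting the times into separate outcomes also adds tests.

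Most of this stands, and it rules out two stronger readings that a reader might infer.

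- **That the plan cuts the product effect to about a third.** This needs an average of exactly the three standardized-session scores, (1 + k)/3, with k = 0. The SAP never proposes that average, and lasting relief at 118 minutes would be a real product effect.
- **That omitting the baseline biases the comparison.** With counterbalanced order it does not by itself do so.

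The count of five ratings also needs a qualification. The tobacco-day list of final questionnaires in Protocol 6.6 leaves out MNWS, QSU and mCES, although the JUUL-day list includes them.

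None of this removes the case for the covariate. It helps under either meaning of the average, and it remains usable if the pre-use QSU is a different form, which a change score does not. Naming one lead outcome answers the worry about added tests.

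**Conclusion.** The point holds as a loss of precision for QSU and MNWS. For a single post-use score, using the pre-use score would cut residual variance by about 9% to 25% and narrow intervals by about 5% to 13%, given an assumed correlation of 0.3 to 0.5. The gain also presumes that the first day's product does not shift the second day's pre-use score differently by sequence.

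Dilution to 60% to 80% of the direct-use effect in scale points is conditional. It arises only if the average is over all five times, and it depends on the assumed effect remaining at 118 minutes. The documents do not show that this reading is intended, but they do not exclude it either. The baseline point does not apply to the mCEQ/mCES.

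**What to change.** In the SAP, Specific Aim 4:

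- State that the pre-use QSU and MNWS scores are never part of the product outcome. Enter each as a same-day covariate, preferably as the within-person difference between days, in the crossover model with product, period and sequence. Do not use a change score.
- Name the 5-minute post-session score as the lead outcome for QSU and MNWS. Report the 118-minute and ad lib scores separately as supporting outcomes.
- Analyse the mCEQ/mCES at its post-use times without a covariate, and use one name for it in both documents.
- Keep the word average only if it means the item or subscale mean, and say so.
- Explain the no-cig tag on the QSU.

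In the protocol, reconcile the tobacco-day list of final questionnaires in 6.6 with the JUUL-day list in 6.5, so that the same times are compared for both products.

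The cost is wording, one degree of freedom per model (28 to 27 for 30 participants in two sequences) and a few more reported outcomes. The scheduled pre-use scores supply the covariate, so no new assessment is needed for it.
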